The NZ Ministry of Health's (MoH) Immunisation Technical Forum (ITF) on vaccines reviewed this recommendation in 2011 and recommended the use of Tdap during pregnancy in NZ (after 20 weeks gestation and preferably prior to 36 weeks).⁵ The MoH also recommends and funds (the vaccine is given at no cost to the woman) influenza vaccination for all pregnant women in NZ.⁶ In 2012, some DHBs in NZ agreed to fund the administration of Tdap during the current pertussis outbreak to pregnant women (30-36 weeks) and to women in the first two weeks after birth.⁷ In October this was extended nationally by the MoH to all women from 28 to 38 weeks gestation for the duration of the epidemic. For General Practices to be paid for administering the vaccines the electronic Practice Management System (PMS) automatically messages through to a central administration centre (Healthpac) once the details of the vaccination have been entered.

As there are limited data on the use of Tdap in pregnant women, NZ is well placed to monitor the safety outcomes in this group.

This study incorporates a study that is currently underway in Canterbury NZ (referred to herein as Study Three⁸—see detail below), assessing the outcomes of mothers receiving Boostrix[®] in pregnancy and their infants up to a year after the birth. It will also provide an infrastructure for another proposed study assessing the antibody response to the primary vaccination series with Infanrix-hexa in infants born to mothers vaccinated with Boostrix[®] during pregnancy.

This is a three-component observational study that will collect data both retrospectively and prospectively. Data for all pregnant women and their infants in NZ between 2009 and 2013 will be obtained and pertussis vaccine exposure during pregnancy verified (Study One). Two sub-studies will actively follow mothers who received Tdap during pregnancy with one also following their infants for one year after birth (Study Two and Three).

Study One will involve de-identified data linkage for all pregnant women and their infants for the period 2009–2013 and the intensive monitoring studies (i.e., Study Two and Three) will prospectively follow up the mother for one month after vaccination (Study Two) with a further group being followed for both maternal and infant outcomes for one year from the birth of the infant (Study Three).

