Rates and patterns of adverse events in women who were administered Tdap during pregnancy

Multiple pregnancies

While the number of visits during pregnancy could have an impact on the pregnancy outcome within the study population in Study Two and Three (but not in Study One). The frequency of prenatal care is a potential confounder as it may be associated both with women receiving Tdap or not, and with birth outcomes. There is no way to capture the number of prenatal visits women have from nationally available data. However, the National Maternity Collection does “contain data on primary maternity services provided under Section 88 of the NZ Public Health and Disability Act 2000. This information is sourced from lead maternity carer claims for payment.” This information might be useable as a proxy to indicate frequency of prenatal care.

Study Three: Intensive monitoring study of pregnant women administered Tdap during pregnancy and their infants

Study Three involves extending and supporting the intensive monitoring study currently being conducted in the Canterbury DHB by [name] (Principal Investigator). Briefly this study runs as per Study Two except the women and their infants are followed up intensively for a period of one year after the birth of the infant. The data collected for the period of one month post vaccination in Study Three will be able to be pooled for the overlapping subset of participants also in Study Two.

Study Three includes women receiving the vaccine under the DHB programme at 30–36 weeks in the Canterbury region.

Figure 1. Study population and outcomes

[figure not shown]
[figure not shown]

Figure 2. Monitoring of pregnant women receiving pertussis during pregnancy

Canterbury DHB continues intensive follow up for birth outcomes and infant outcomes for one year for a sample of 300 women and their infants. Infant follow up at three to seven months and 12 months of age in this DHB as per Canterbury protocol (Study Three) (Appendix 8).

Study procedures

Study One (utilising whole population data-linking)

Data sets for hospitalisations, pertussis notifications, infant vaccination and maternal Tdap vaccination will be obtained for the period 1 January 2009 to year ending 2013 from the following national databases:

- National Minimum Dataset for hospitalisation data
- The National Immunisation Register for infant immunisation data
- Notification data from the ESR
- Pregnancy Immunisation records from the HealthPAC claims database

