Vaccinee data verified as non-duplicated, then NHI number, name and phone number will be replaced by a sequential number (These are the only variables that contain personal identifiable information and will also be used to ensure there is no duplication of survey and extraction of maternal and pregnancy data at the end of the study).

Data set validation

Data set will be double entered for validation

Any corrections will be reviewed by a third party

Data confidentiality

No names or NHI numbers will be published

Visibility of the National Health Index number (NHI) of the participant's records will be password protected and restricted to the key investigators before being removed at the end of the study.

Access to complete data sets will be limited to the investigators and data analysts.

Data storage

The datasets will be stored in a password-protected file within The University of Auckland and the physical files will be held in a locked filing cabinet by the Principal Investigator/s [name] who will store it for 10 years in accordance with the NZ ethical guidelines.

Study duration

	Intensive study	Population datalink study
Month one	First participants enrolled in intensive study	
Month six	Last participants enrolled in intensive study (this potentially may be extended depending on enrolment)	Preparation for population data collection. Obtain ethical approval
Month 12	Interim report due	Receive 2009-2013 data, commence data cleansing and data matching
Month 18	Last of the 1 year follow up data will be collected	Commence analysis
Month 20	Final study report due	
Month 22	Submission of publication	
Month 24		Final report
Month 28		Submission of publication

Statistical analysis and sample size justification

Study One (N=~325,000)

Sample size:

Over the five-year period of this study there will be approximately 325,000 births. The percentage vaccinated will increase over the time period as the funded vaccine is promoted over the epidemic but on average approximately 30% of mothers would be expected to have received vaccination during pregnancy.

Analysis:

Logistic regression will be used to estimate odds ratios for the risk for (specific) adverse events for both mothers and infants in vaccine exposed and unexposed groups. Age, ethnicity and socioeconomic deprivation and season for hospital admission will be included as additional explanatory variables.

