As specific diagnoses are not necessarily independent events each person will only be counted once for each hospitalisation, the primary diagnosis and repeat admissions for the same episode will be removed, including transfers from one hospital to another.

For diagnosis where individuals may have multiple admissions for different occurrences and the outcome is a count, Poisson regression will be used with testing and adjustment for overdispersion where required.

The temporal relationship between onset of events and vaccination will be presented including distribution where appropriate,

Serious adverse events will be reported as detailed clinical cases.

To analyse the effect of Tdap on still births we will perform a survival analysis. The time dependent explanatory variable of vaccination status and 'failure' of still birth and censored at birth, also including demographics as explanatory variables. The independent explanatory variable will be Tdap vaccination status of the mother (time dependent). Time will commence at the beginning of the inclusion time for an individual— 28(20) weeks gestation. Women will be censored at time of live birth or at the end of the study period, 31 December 2013, whichever occurs first.

Study Two (N=~300)

Estimated number of women receiving pertussis vaccine during pregnancy for study period, potential study population

The birth cohort in NZ is approximately 65,000 per annum. Tdap is funded for pregnant women, but it is difficult to estimate how many women will take up the vaccine. In one DHB with a birth cohort of 6,000 who were first to offer pertussis vaccine free to pregnant women, 220 claims for the Tdap vaccine had been lodged in six weeks and 1,164 over eight months. At the 10th June 2012, out of 255 claims processed at that time 22 (9%) of women had not consented to follow up. The number of women able to be recruited to the Canterbury study is limited by available nurse time.

Based on the experience in Canterbury assuming sufficient workforce capacity the potential number of women available for follow up over a one-year period is:

National birth cohort 65,000

Uptake of pertussis vaccine in pregnancy 10–40%

Potential annual vaccinated cohort 6,500–26,000

Likely to consent (90%) 5,850–23,400

Eligible to participate (87%) 5,090–22,620

- Participation by general practices (success in obtaining informed consent to follow up) estimate 30–90% (likely to be higher rather than lower)

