It is anticipated that the difference in AEs between subgroups in the trial will be small. As this is an observational study we therefore plan to describe the confidence intervals for the proportions of AEs within each group. A sample size of 300 produces a two-sided 95% confidence interval with a width equal to 0.081 when the sample proportion is 0.150.

Women who have multiple pregnancies and/or complicated pregnancies will be excluded from the final analyses and described separately.

Total expected participants

	Study population	Sample size	
--	------------------	-------------	--

Study One	325,000		Total pertussis-vaccinated maternal population
Study Two	1,527–20,358	300	~300 pertussis vaccinees
Study Three	6,000	300	300 pertussis vaccinees

Vaccines

Pertussis vaccine

The pertussis vaccine funded for pregnant women is Boostrix[®]. There are other licensed vaccines but no other pertussis vaccines currently funded for pregnant women in NZ.

Specific vaccine supply requirement

N/A. This is an observational study. There are no vaccine requirements for this study.

Adverse experience reporting

Adverse Event data are being accessed/collected during this project in Study Two and Three.

The Investigator will report SAEs (either initial or follow-up reports) to:

The NZ Centre for Adverse Reaction Monitoring (CARM) at the University of Otago according to local requirements. (See Appendix 9, contract Exhibit D, CARM Reporting Form)

The Ethics Committee according to requirements

The Marketing Authorisation Holder within 24 hours according to contracted safety reporting requirements defined in the study contract. Case reporting will include the relevant variables in the GSK “with intensity GCSP reporting form”. (See Appendix 10)

Administration during pregnancy is relevant in the age group, so pregnancy reporting is expected to be relevant. All participants will be pregnant.

There will be no causality assessments conducted during this study as this is observational and there is no intervention.

Any adverse events that are reported to the NZ Centre for Adverse Reaction Monitoring (CARM) undergo causality assessment. This data is provided to the WHO and the MoH.

CARM is the official regulatory body in charge of receiving all adverse event reports in NZ. CARM collaborates with and pools anonymised data, together with other national monitoring centres, into the database of the World Health Organization's International Drug Monitoring Programme.

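### Study One's planning figure of about 30% of mothers vaccinated over 2009–2013 cannot be reconciled with the protocol's own funding dates and 10–40% uptake; about 2.5–12% of births, at most about 16%, is what they support

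*Protocol*

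**What the plan says.** In the protocol's statistical section, the Study One paragraph begins: "Over the five-year period of this study there will be approximately 325,000 births". It adds that the vaccinated percentage will rise over time, and that "on average approximately 30% of mothers would be expected to have received vaccination during pregnancy". No significance level, detectable effect or power is given for Study One.

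Other sections supply the facts that bear on this figure:

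- **Window.** Data are requested "for the period 1 January 2009 to year ending 2013" (Study procedures, Study One). The stillbirth analysis censors "at the end of the study period, 31 December 2013".
- **Funding.** Of the funded programmes, the Background says: "In October this was extended nationally by the MoH to all women from 28 to 38 weeks gestation". The Study One population section gives the year as 2012. It adds that some DHBs funded the vaccine earlier in 2012 and that those exposures can be identified. Before that the vaccine had to be bought privately; such use was very low and cannot be identified.
- **Births and uptake.** The Study Two section says: "The birth cohort in NZ is approximately 65,000 per annum". Its recruitment projection lists "Uptake of pertussis vaccine in pregnancy 10–40" per cent, or 6,500–26,000 women a year.
- **Participants table.** The Study One row carries 325,000 and, in a column without a heading, "Total pertussis-vaccinated maternal population".

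**The concern.** The 30% is worded as an average over all five birth years, yet for more than three of those years there was no funded programme. A percentage of this size is plausible as uptake while the vaccine is funded, but not as the exposed share of the whole 2009–2013 cohort.

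The exposed share matters for secondary objectives 1 and 2, which compare vaccinated with unvaccinated women and their infants. With the total fixed by the registers, precision in those comparisons depends largely on the number exposed. The clinical hypothesis is that event rates are similar. If the expected number exposed is overstated, an imprecise null result on a rare outcome such as stillbirth could be read as more reassuring than it is.

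**Working it through.** **Reproducing the plan's figures.** 5 years × 65,000 = 325,000 births, as stated. 0.30 × 325,000 = 97,500 vaccinated mothers. That number is implied, not printed.

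**Formula.** Exposed share = uptake × births offered funded vaccine ÷ 325,000, where births offered = 65,000 × funded months ÷ 12.

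**Inputs.** Uptake is 10–40% (Study Two). National funding from October 2012 to December 2013 is 15 months. The regional start is not dated beyond 2012. Mid-April is taken from the Canterbury media release of 19 April 2012 cited in the Background, and January 2012 is used as the extreme. The regional share of births is not given, so it is varied: 9% is Canterbury alone (6,000 ÷ 65,000), and 50% and 100% are assumptions. From mid-April to the end of September 2012 is 5.5 months, or 29,792 births nationally.

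| Births counted as offered funded vaccine | Births | Share of 325,000 | Uptake needed for 30% | Exposed at 10–40% uptake |
|---|---|---|---|---|
| National programme only, 15 months | 81,250 | 25.0% | 120% | 8,125–32,500 (2.5–10.0%) |
| Plus regional from mid-April 2012, 9% of births | 84,000 | 25.8% | 116% | 8,400–33,600 (2.6–10.3%) |
| Plus regional from mid-April 2012, 50% of births | 96,146 | 29.6% | 101% | 9,615–38,458 (3.0–11.8%) |
| All DHBs from mid-April 2012, 20.5 months | 111,042 | 34.2% | 88% | 11,104–44,417 (3.4–13.7%) |
| All DHBs from January 2012, 24 months | 130,000 | 40.0% | 75% | 13,000–52,000 (4.0–16.0%) |

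Counting every birth from January 2011 (36 months, 195,000 births) at 40% uptake, which goes beyond anything the protocol says was funded, still gives only 78,000 (24%). Put another way, at the protocol's maximum of 26,000 vaccinated women a year, 97,500 would take 97,500 ÷ 26,000 = 3.75 years of full national funding. The window holds 1.25.

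**Effect on precision.** For a fixed total and a rare outcome near the null, the standard error of a log odds ratio is proportional to 1/√[p(1−p)], where p is the exposed share. Relative to p = 0.30:

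- p = 0.16: √(0.21 ÷ 0.1344) = 1.25
- p = 0.10: √(0.21 ÷ 0.09) = 1.53
- p = 0.075: √(0.21 ÷ 0.0694) = 1.74
- p = 0.025: √(0.21 ÷ 0.0244) = 2.94

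**Illustration on assumed background risks** (unadjusted, two-sided 5%, 80% power, total 325,000). The protocol gives no such risks for Study One.

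| Assumed background risk | Detectable OR at 30% exposed | At 10% exposed | At 2.5% exposed |
|---|---|---|---|
| 1% | 1.11 | 1.17 | 1.33 |
| 0.1% | 1.36 | 1.56 | 2.14 |

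**The case against.** Several points can fairly be made on the other side.

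- **The dates alone do not exclude 30%.** A reader might infer that they do, because national funding covers only 25% of births. Regional exposures in 2012 also count, and if all DHBs were funded from January the ceiling is 40%. This stands: excluding 30% also needs the uptake range. That range is a Study Two recruitment projection which the protocol itself calls difficult to estimate. Even so, the most generous reading of 2012 needs 75% uptake, nearly twice the stated maximum.
- **A flat 2.5–10% is not the right replacement.** It leaves out regional exposures that the protocol says it can identify. This stands, and because the regional share of births is not given, only a range under stated assumptions can be offered.
- **No power claim falls.** A reader might infer that Study One's power is invalidated. None is stated. The Background's remark that the retrospective component adds power to the overall study remains true even at 8,125 exposed, against about 600 women in Studies Two and Three. The cohort size comes from registers, so no recruitment or analysis step depends on the 30%. All of this stands.
- **The table may not be wrong.** It can be read as calling all 325,000 women vaccinated. The label sits in an unheaded column, parallel to the vaccinee counts of the other two studies, in a table damaged by text extraction. It may only describe which vaccinees Study One covers. It is ambiguous, not a demonstrated error.
- **The authors may have meant uptake while funded.** The sentence does mention promotion of the funded vaccine, and 30% lies within 10–40%. But it refers to the five-year period and to an average over that time, so the five-year reading is the natural one. If the other was intended, the wording still needs changing.

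**Conclusion.** The planning figure is wrong as written. No combination of the protocol's funding dates with its 10–40% uptake reaches a five-year average of 30%. The supported range is roughly 2.5–12% of births, and about 16% at the extreme, so 30% overstates the exposed share by about 1.9-fold (30 ÷ 16) to 12-fold (30 ÷ 2.5). The conclusion rests on even births across the year, negligible identifiable exposure in 2009–2011, and uptake no higher than 40% under funding.

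The consequence is limited to expected precision in the secondary vaccinated-versus-unvaccinated comparisons. The Study One objective of establishing background rates is unaffected.

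A reader might also infer that 30% was carried over from Canterbury, where 1,164 claims in eight months against 6,000 × 8/12 = 4,000 births is 29.1%. The protocol does not say so, and since Canterbury also funded vaccination in the first two weeks after birth, those claims may include postpartum doses. The inconsistency does not depend on where the figure came from.

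**What to change.** In the Study One sample-size paragraph, replace the 30% with an expected exposed number by calendar period: none or negligible in 2009–2011, regional programmes in 2012, and the national programme from October 2012. State the assumed uptake and the assumed regional share of births for each period. On the protocol's present figures the total comes to roughly 2.5% to 12% of births, and at most about 16%.

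Then state the precision or detectable odds ratio that these numbers give for secondary objectives 1 and 2, with the assumed background risk of each outcome. In the participants table, make clear that 325,000 is all births, vaccinated and unvaccinated, and show the expected number vaccinated separately.

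The cost is wording and a short calculation. Data sources, cohort definition and analysis methods do not change, but the stated exposed number becomes less favourable.

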The large retrospective component to this study adds significant power to the overall study: It is a cost effective method of data collection and enables more effective assessment of seasonality. It will also provide data on a range of pregnancy and birth outcomes which are not readily available from a prospective study design (e.g., Apgar scores).

⁵ New Zealand Ministry of Health. Current advice on the public health management of pertussis. Wellington: MoH; 5 April 2012. Available at http://www.nzdoctor.co.nz/media/1682109/pertussis_letter_moh_5_apr_2012.pdf

⁶ New Zealand Ministry of Health. Chapter 15: Influenza. In Immunisation Handbook 2011. Wellington: MoH; 2011. Available at

http://www.google.co.nz/url?sa=t&rct=j&q=ministry%20health%20influenza%20vaccine%20pregnant%20women%20funded%20&source=web&cd=7&ved=0CGYQFjAG&url=http%3A%2F%2Fwww.health.govt.nz%2Fsystem%2Ffiles%2Fdocuments%2Fpublications%2F15influenza.pdf&ei=8SiWT8iDH4_m8QQgnNGMCG&usq=AFQjCNFUuAYDXQKxJFmqXKd4PBfzm1i2A

⁷ Canterbury District Health Board. Media release from Canterbury DHB: Free whooping cough vaccine extended to pregnant women. Christchurch: CDHB; April 19, 2012.

⁸ Study Three is largely funded by Canterbury DHB, but is being conducted as part on the three-component study covered in this protocol. Study Three runs as per Study Two, except the former study will follow women and their infants for a period of one year after the birth of the infant while the follow up for the latter study is to four weeks post vaccination.

Study design

Study One: Retrospective analysis of safety outcomes for pregnant women vaccinated with TdaP vaccine and their infants.

Study population

All women delivering in NZ for the study period 2009–2013 and their infants will form the overall study population. Study One will identify all pregnancies and all exposures (except the very few who privately purchased the vaccine).

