All participants in this study will be de-identified.

Outcomes

Hospitalisation outcomes of interest will include the following conditions.

Mother	ICD-10-CM
Still birth, preterm birth pregnancy complications	P95 Stillbirth ⁹ O60 Preterm labour Z37 Outcome of delivery 
 • Single stillbirth • Twins, one liveborn and one stillborn • Twins, both stillborn • Other multiple births, all stillborn O00-O99.9 Pregnancy, childbirth and the puerperium
Infant	
Certain conditions originating in the perinatal period	Newborn affected by maternal factors and by complications of pregnancy, labour, and delivery P00-P96
Early neonatal death, SIDS	Ill-defined and unknown causes of mortality R95-R99.9
Congenital anomalies (CVS, CNS, other)	Congenital malformations, deformations and chromosomal abnormalities Q00-Q99.9
Infectious Diseases (pertussis, , etc.)	Certain infectious and parasitic diseases A00-B99
Meningitis	Meningitis due to other and unspecified causes G03 
 •arachnoiditis NOS •leptomeningitis NOS •meningitis NOS •pachymeningitis NOS
Encephalitis	Encephalitis, myelitis and encephalomyelitis G04 
 •acute ascending myelitis •meningoencephalitis •meningomyelitis
Lower respiratory (bronchiolitis, asthma, pneumonia, acute unspecified LRTI, bronchiectasis, Acute bronchitis, lung abscesses/pyothorax	Diseases of the respiratory system J00-J99
Neurological	Diseases of the nervous system G00-G99

⁹ Information about stillbirths is recorded in the Mortality Collection. The Mortality Collection includes extra information about fetal and infant deaths, such as gestation and birth weight. The ICD codes we propose are: P95 Fetal death of unspecified cause Z37 Outcome of delivery, Z37.1Single stillbirth, Z37.3 Twins, one live born one stillborn, Z37.4 Twins, both stillborn, Z37.7 Other multiple births, all stillborn

Pregnancy duration will be classified using the gestational age field from the National Maternity Collection data set. This field gives the duration of pregnancy in number of completed weeks. Preterm will be defined as birth before 37 weeks gestation. Normal term will be defined as birth between 37 and 41 weeks gestation. Post-term will be defined as birth after 41 weeks gestation.

The following codes are available so we can get banded weeks of gestation.

1518 Duration of pregnancy

Code	Number	
O09.0	<5	Completed weeks
O09.1	5-13	Completed weeks

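### Study One's infant logistic models have no provision for twins sharing one mother and one exposure, so intervals for infant outcomes concentrated in multiples would be somewhat too narrow

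*Protocol*

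**What the plan says.** All references are to the Protocol.

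- **Population** (Study design, Study One, Study population): "All women delivering in NZ for the study period 2009–2013 and their infants will form the overall study population". Multiples are not excluded. The stillbirth codes in the Outcomes table include "Twins, one liveborn and one stillborn".
- **Size and exposure** (Statistical analysis, Study One, Sample size): "Over the five-year period of this study there will be approximately 325,000 births", and "on average approximately 30% of mothers would be expected to have received vaccination during pregnancy". The first figure counts births, the second mothers.
- **Binary outcomes** (Study One, Analysis): "Logistic regression will be used to estimate odds ratios for the risk for (specific) adverse events for both mothers and infants". The listed covariates are age, ethnicity, deprivation and season. Plurality is not among them, and no variance estimator is named.
- **Counts** (same section): "Poisson regression will be used with testing and adjustment for overdispersion where required".
- **Non-independence** (same section): "As specific diagnoses are not necessarily independent events each person will only be counted once for each hospitalisation", with repeat admissions for one episode and transfers removed. There is no other rule of this kind.
- **Stillbirth** (same section): a survival model on women with time-dependent vaccination status, failure at stillbirth and censoring at live birth.
- **Identifiers** (end of the Outcomes section): each birth, in hospital or not, receives its own NHI number. Hospital and notification records are matched to vaccine status on that number (Study participants).
- **Contrast**: Study Three removes multiple pregnancies from its final analyses and describes them separately. The heading on multiple pregnancies under Study Two is followed only by text on antenatal visits.

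**The concern.** Twins have the same mother and the same vaccination status, and many of their perinatal outcomes are strongly correlated. A logistic model that treats them as two unrelated infants credits the data with more information than they hold. The standard error of the exposure odds ratio is then too small and the nominal 95% interval covers less than 95%.

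The Protocol does take up non-independence, but its remedy stops at the person. Because each twin has a separate NHI number, the pair passes that rule as two persons.

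This matters because the clinical hypothesis is that event rates are similar with and without vaccination. A conclusion of similarity, or of a small difference, rests on intervals with their stated coverage. The outcomes most exposed are infant outcomes much commoner in multiples, chiefly P00–P96.

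**Working it through.** **The Protocol's own figure.** "The birth cohort in NZ is approximately 65,000 per annum" (Study Two, estimated number of women). Over five years, 65,000 × 5 = 325,000, which reproduces the Study One total. The Protocol gives no Study One power, interval width, twin rate or within-pair correlation, so everything below rests on assumed inputs, shown as ranges.

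**Twin effect.** Let f be the share of infants who are twins, p_s and p_t the risks in singletons and twins, and ρ the within-pair correlation. Overall risk is p = (1 − f)·p_s + f·p_t. Take the null effect, with exposure shared by the pair and unrelated to plurality. Compare the variance that sums residuals over each pregnancy with the independence variance p(1 − p) per infant:

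variance ratio = 1 + f·[ρ·p_t(1 − p_t) + (p_t − p)²] / [p(1 − p)]

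SE ratio = square root of the variance ratio; actual coverage = 2Φ(1.96 / SE ratio) − 1.

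**Worked case**: perinatal-type outcome, f = 0.03, p_s = 0.10, p_t = 0.45, ρ = 0.6.
- p = 0.97 × 0.10 + 0.03 × 0.45 = 0.1105, so p(1 − p) = 0.0983.
- Bracket: 0.6 × 0.45 × 0.55 + 0.3395² = 0.1485 + 0.1153 = 0.2638.
- Variance ratio: 1 + 0.03 × 0.2638 / 0.0983 = 1.081. SE ratio 1.039, coverage 94.1%.

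**Range of assumptions**

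| Infant outcome (p_s, p_t, ρ) | SE ratio at f = 2%, 3%, 4% | Coverage |
|---|---|---|
| Same risk (5%, 5%, 0.3) | 1.003, 1.004, 1.006 | 94.9% |
| Same risk (5%, 5%, 1) | 1.010, 1.015, 1.020 | 94.8–94.5% |
| Perinatal type (10%, 45%, 0.6) | 1.027, 1.039, 1.050 | 94.4–93.8% |
| Fully shared (6%, 50%, 1) | 1.066, 1.091, 1.113 | 93.4–92.2% |
| Fully shared (5.5%, 60%, 1) | 1.082, 1.111, 1.136 | 93.0–91.6% |

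The last two rows describe preterm birth counted once per infant. They do not apply if it is counted once per pregnancy.

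**Repeat pregnancies.** These were simulated separately: 20,000 women, 3,000 replicates, 20% or 35% of women with a second pregnancy, a 4% risk for a woman with zero random effect, and a woman-level standard deviation of 1.5 on the logit scale. The empirical SE of the log odds ratio was divided by the mean model-based SE.
- Exposure following calendar time (2% in the first and 50% in the second pregnancy of women with two): 0.996 and 1.000.
- Exposure identical in both pregnancies: 1.026 and 1.033.

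With 3,000 replicates the simulation error of such a ratio is about 1/√6000 = 1.3%, so the first pair cannot be told apart from 1.

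**The case against.** The strongest objection is that this is silence and not an error. The Protocol names model families and covariates, names no variance estimator, and nowhere says that siblings are treated as independent. A cluster-robust variance often appears in the statistical analysis plan, which is not at hand. This stands in part: the point is a method to be fixed, and a plan that already clusters on the mother closes it. It does not remove the point, because the Protocol addresses non-independence explicitly and sets its rule at a level that twins pass as two persons.

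A reader might also infer that the intervals for preterm birth and stillbirth are invalid, with coverage of 92–93%. The Protocol does not support that. Both outcomes are listed under the mother, the delivery-outcome codes describe a whole twin delivery in one code, and stillbirth has a survival model on women. Counted once per pregnancy, they do not duplicate twins.

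Nor are the count models plain Poisson. The overdispersion adjustment may absorb part of the extra variance, although it is not a cluster correction and does not reach the logistic models.

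Finally, a reader might infer that repeat pregnancies also make the intervals too narrow. National funding began only in October 2012 (Study population), so exposure will often differ between one woman's pregnancies. On that pattern the simulation shows essentially no effect.

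**Conclusion.** The point holds for the infant models. Multiples are in the analysis, twins count as separate persons, and the one stated safeguard does not link them. Under independence standard errors, intervals for infant outcomes concentrated in multiples would be too narrow by a modest amount. The true SE is about 1.03–1.05 times the model-based one for a perinatal-type outcome (coverage about 94%) and at most about 1.02 times for outcomes equally common in twins and singletons. The 1.07–1.14 range applies only to a fully shared outcome analysed per infant, which the Outcomes table does not indicate for preterm birth.

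All these sizes depend on assumed twin shares of 2–4% and on assumed risks and correlations. None comes from the Protocol. The direction for repeat pregnancies is not established.

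The unit of analysis does need stating. The total is in births and the exposure share in mothers. P95 stands under the mother but also falls within the infant range P00–P96. A twin delivery with one live birth and one stillbirth meets both the failure and the censoring condition of the stillbirth model for the same woman.

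**What to change.** 1. Use cluster-robust or GEE standard errors, clustered on the mother, for the infant logistic and Poisson models. This also covers repeat pregnancies, whichever way they act.
2. Keep a de-identified mother key through the linkage. Study One data are de-identified, so this has to be arranged before the linked files are made.
3. State the unit of analysis for each outcome, with preterm birth and stillbirth analysed once per pregnancy, and say where P95 is counted.
4. Give a rule for discordant twins in the stillbirth survival model.
5. Add a singleton-only sensitivity analysis.

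The cost is slightly wider intervals for some infant outcomes and a little extra linkage and analysis work. No new data are needed beyond the mother–infant link that assigning maternal vaccination status to infants already requires.
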